#### **2.8.3.2 Vital signs**

All vital signs measurements will be listed for subjects who fulfil at least one of the following clinically notable criteria:

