8.4 Safety

Safety evaluation will include ocular and non-ocular assessments (eg vital signs, IOP, slitlamp and ophthalmoscopy) and will be performed according to the clinical practice. Any clinically significant changes should be reported as AEs.

For details on AE collection and reporting, refer to [Section 10.1.1](#).

The End of Study visit after 7 days (\pm 2) will be done at the site. The ocular assessments like slitlamp and ophthalmoscopy will be recorded in the source document and IOP will be entered in the eCRF. The non-ocular assessment (vital signs) will be recorded in the eCRF.

Additionally, a follow-up phone call 30 days after the End of Study Visit will be performed for subjects with any ongoing AEs at the End of Study Visit. Any occurred adverse events in this period should be collected in the source, and SAEs must be reported to Novartis safety according instructions in [Section 10.1.3](#).

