### 1.1 Study design

This study is an open-label, single arm, multicenter, phase IIIb study. Screening and Baseline visits may be performed on the same day. The Follow-up, which is End of Study is 7 days  $\pm$  2 days after Baseline.

Subjects who consent will undergo all screening activities to evaluate their eligibility based on the inclusion and exclusion criteria. Subjects who meet all inclusion criteria and none of the exclusion criteria will receive:

- Brolucizumab 6 mg prefilled syringe (PFS), one injection.

The study population will be male and female subjects  $\geq$  50 years old who are diagnosed with neovascular age-related macular degeneration (nAMD). Approximately 30 subjects are expected to be injected at approximately 3 sites in the United States of America.

Randomization is not applicable for this open-label study.

The primary analysis will be conducted after database lock (DBL).

No interim analyses are planned.

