## 2 Statistical methods

### 2.1 Data analysis general information

The final analysis will be performed by Novartis using SAS Version 9.4.

Categorical variables will be presented as frequencies and percentages. For continuous data, the mean, standard deviation, median, lower quartile, upper quartile, minimum and maximum will be presented.

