### **2.1.1.3 Post-baseline definition**

Post-baseline measurements are defined as assessments after the injection of study treatment.

When change from baseline is of interest the following formula will be used for each scheduled visit where baseline and post-baseline values are both available:

Change from baseline = post-baseline value – baseline value

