## **2.5.2 Statistical hypothesis, model, and method of analysis**

No formal hypothesis testing will be performed in this study.

See [Section 2.8.1](#) for details of the analyses to be performed for AEs.

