### **2.8.3 Other safety data**

#### **2.8.3.1 Intraocular pressure (IOP) (mmHg)**

All IOP measurements will be listed for subjects who fulfil at least one of the following criteria:

- IOP  $> 30$  mmHg
- Increase  $\geq 10$  mmHg from pre-injection IOP to post-injection IOP within a visit

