## 3 Sample size calculation

No formal statistical power calculations to determine sample size were performed for this study.

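### SAP 2.8.3 lists IOP and vital signs only for subjects who cross a threshold, so sub-threshold shifts not reported as AEs, and the number evaluable, cannot be seen

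*SAP*

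**What the plan says.** **Planned output.** SAP 2.8.3.1 states: "All IOP measurements will be listed for subjects who fulfil at least one of the following criteria". The criteria are an IOP above 30 mmHg, or a rise of at least 10 mmHg from before to after the injection within one visit. SAP 2.8.3.2 states: "All vital signs measurements will be listed for subjects who fulfil at least one of the following clinically notable criteria". Table 2-1 then gives high and low limits for systolic pressure, diastolic pressure and pulse. Most combine an absolute value with a change from baseline. Nothing else is planned for these variables.

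**General conventions.** SAP 2.1 says: "For continuous data, the mean, standard deviation, median, lower quartile, upper quartile, minimum and maximum will be presented". SAP 2.1.1.3 says: "When change from baseline is of interest the following formula will be used". Age (SAP 2.3.2) is the only variable that the SAP says it will summarise as continuous.

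**Protocol.** Section 8.4 says: "Safety evaluation will include ocular and non-ocular assessments", and names vital signs and IOP among them. It also asks for clinically significant changes to be reported as AEs. Table 8-1 has IOP and vital signs entered in the clinical database at Baseline and Day 8; slit-lamp and ophthalmoscopy findings stay in source documents. Section 12.4.2 planned to list pre- and post-injection IOP and all vital signs, with abnormal vital signs flagged and no filter on who is listed.

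**Declared change.** SAP section 4 states openly that both listings are now restricted to subjects who meet a criterion. It gives no reason for this, although it cites small sample size for two other reductions.

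**The concern.** Safety is the trial's only objective, and IOP and vital signs are its only quantitative safety measurements in the database. A listing filtered on individual thresholds says nothing about subjects below them, wherever the thresholds are set. If few or no subjects are listed, a reader of these outputs cannot tell whether values were unchanged, rose consistently by a moderate amount, or were not measured in some subjects. The protocol's full listing of about 30 subjects would have let a reader count the measured subjects and work out the shift. The SAP removes that and puts no summary in its place.

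**Working it through.** The documents give no power or precision figure to reproduce (SAP section 3: "No formal statistical power calculations to determine sample size were performed for this study"). The check has four steps.

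**1. What the criteria let through (no distributional assumption).**
- *Systolic pressure.* Protocol exclusion 10 admits a baseline of up to 160. A move from 160 to 190 is a rise of 30, which is not more than 30, and 190 is not above 200. Not listed.
- *Diastolic pressure.* The ceiling is 100. A move from 100 to 115 is a rise of 15, which is not more than 20, and 115 is not above 115. Not listed.
- *IOP at Day 8.* No injection is given at Day 8, so the 10 mmHg criterion does not apply to a change between visits. A move from 15 at Baseline to 30 at Day 8 is not above 30. Not listed.
- *IOP within the injection visit.* A uniform rise of 9 mmHg lists nobody if every pre-injection value is at most 21 (21 + 9 = 30, and 9 is below 10).

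**2. How often no IOP criterion is met.** From the documents: n = 30 (SAP 1.1: "Approximately 30 subjects are expected to be injected at approximately 3 sites in the United States of America"). Assumed, because the documents give no values: baseline IOP normal with mean 15 and SD 3; change independent of baseline, normal with mean 4 and SD s of 3, 4 or 5.

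*Rise at Day 8.* The Day 8 value has mean 15 + 4 = 19 and SD √(9 + s²). With p the probability that it exceeds 30, P(none listed) = (1 − p)^30.

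| s | SD of Day 8 value | z = 11/SD | p | (1 − p)^30 |
|---|---|---|---|---|
| 3 | 4.243 | 2.593 | 0.00476 | 87% |
| 4 | 5.000 | 2.200 | 0.01390 | 66% |
| 5 | 5.831 | 1.887 | 0.02961 | 41% |

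*Rise within the injection visit.* A subject stays unlisted only if the change is below 10 and the post-injection value is at most 30. The first condition alone gives Φ(6/s)^30, which is 50%, 13% and 3%. With both, the probability that one subject stays unlisted (by numerical integration) is 0.9750, 0.9304 and 0.8820. Raised to the power 30, this is **47%, 11% and 2%**.

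Simulation of the same model gives 87%, 65% and 41% for Day 8, and 47%, 12% and 2% within the visit. The one-point differences are sampling error.

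**3. What a summary would show.** The 95% CI half-width for the mean change is t(0.975, 29) × s/√30 = 2.045 × s/5.477. This is 1.12, 1.49 and 1.87 mmHg for s = 3, 4 and 5. A mean rise of 4 mmHg lies 4/1.87 = 2.1 to 4/1.12 = 3.6 half-widths from zero.

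**4. The denominator.** If nobody of n evaluable subjects meets a criterion, the exact two-sided 95% upper limit for the rate is 1 − 0.025^(1/n): 11.6% for n = 30, 13.7% for n = 25 and 16.8% for n = 20. The SAP reports the number treated (2.4.1) but not the number with IOP or vital signs measured, so a reader could not tell which limit applies.

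**The case against.** The strongest case on the other side has five parts.

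- *Important changes are not lost.* Protocol 8.4 sends clinically significant changes to AE reporting, and SAP 2.8.1 tabulates AEs by number and percentage. This stands and limits the point. A reader might infer that a deterioration in IOP or blood pressure could go wholly unreported, or that the paired data are discarded. The documents support neither: the AE route exists, and the data remain in the database.
- *The general sections promise nothing.* SAP 2.1 is a presentation convention and SAP 2.1.1.3 is conditional. Table 2-1 does use change from baseline, as a flag for blood pressure and pulse. This stands: the SAP does not break a commitment, and change from baseline is not unused. It is only never summarised.
- *The protocol planned no summaries, and the change is declared.* Both are true, so this is not a hidden deviation. What is lost against the protocol is the full listing.
- *A substantial post-injection rise would usually be listed.* For a 4 mmHg rise within the injection visit this holds at an SD of change of 4 or 5. A reader might infer that an empty listing is the usual result after any systematic rise. That holds mainly for Day 8, and at SD 5 not even there. When someone is listed, though, the output still gives no mean and no denominator.
- *A CI has limited use here.* SAP 2.5.2 says: "No formal hypothesis testing will be performed in this study". With one arm, a change cannot be attributed to the syringe. Because entry is capped at 160/100, regression to the mean alone could raise blood pressure at Day 8. This stands: any interval must be labelled descriptive.

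**Conclusion.** The point holds in a limited form and is minor. SAP 2.8.3 and section 4 replace unfiltered listings with filtered ones and add no number evaluable, no rate and no summary of value or change. The gap covers sub-threshold shifts that no investigator reports as AEs, and the missing denominator. The primary endpoint, AE incidence, is unaffected.

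The unlisted moves in step 1 and the missing denominator follow from the documents alone. The chances in step 2 rest on assumed means and SDs and on normality, and they range from 87% down to 2% with the timing and spread of the rise. They show that a shift can go unseen, not that it usually will. No corresponding chance is given for vital signs, because that listing opens on any of three variables and the documents give no distribution for them.

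**What to change.** Keep both listings and add to SAP 2.8.3 a descriptive table for study-eye IOP (pre-injection, post-injection, Day 8) and for systolic pressure, diastolic pressure and pulse (Baseline, Day 8). For each variable, show:

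- the number evaluable at each time point;
- the SAP 2.1 statistics for the value and for change from baseline;
- n/N (%) meeting each existing criterion, with N the number evaluable.

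If a 95% CI for the mean change is included, label it descriptive and state that a single-arm change cannot be attributed to the syringe.

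At minimum, restore the protocol's unfiltered listing. For about 30 subjects it would show every paired value and every missing one.

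The cost is SAP wording and one or two tables from data already in the eCRF. No new data and no protocol amendment are needed. The downside is slightly more output for a small study.

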**Table 2-1 Clinically notable criteria for vital signs**

Variable	Category	Critical Values
Systolic blood pressure (mmHg)	High	Either $>180$ with an increase from baseline $>30$ or $>200$ absolute
	Low	Either $<90$ with a decrease from baseline $>30$ or $<75$ absolute
Diastolic blood pressure (mmHg)	High	Either $>105$ with an increase from baseline $>20$ or $>115$ absolute

Variable	Category	Critical Values
	Low	Either <50 with a decrease from baseline > 20 or <40 absolute
Pulse rate (bpm)	High	Either >120 with an increase from baseline of >25 or >130 absolute
	Low	Either <50 with a decrease from baseline >30 or <40 absolute

## 2.9 Other Exploratory analyses

No exploratory objectives are defined for this study.

## 2.10 Interim analysis

No interim analysis is planned for this study.

## 3 Sample size calculation

No formal statistical power calculations to determine sample size were performed for this study.

## 4 Change to protocol specified analyses

Protocol section 12.2 states that relevant medical histories and current medical conditions at baseline will be summarized. Given the small sample size this data will be listed only.

Protocol section 12.3 states that descriptive statistics for exposure to study treatment and the cumulative number of injections will be presented. As subjects are only scheduled to receive a single injection of study treatment the total number of patients who received an injection will be presented.

Protocol section 12.3 states that concomitant medications and significant non-drug therapies prior to and after the start of the study treatment will be summarized. Given the small sample size this data will be listed only.

Protocol section 12.4.2 states that treatment emergent AEs will be summarized by SMQ and PT. This summary will not be produced, treatment emergent AEs will be presented by SOC and PT only.

Protocol section 12.4.2 states that AE presentations will be presented for the fellow eye. Adverse events for the fellow eye will be listed only.

Protocol section 12.4.2 states that pre-injection and post-injection IOP measurements will be listed. Instead, IOP measurements will only be listed for subjects who have at least IOP measurement meeting the criteria defined in SAP [Section 2.8.3.1](#).

Protocol section 12.4.2 states that all vital signs data will be listed. Instead, vital signs measurements will only be listed for subjects who have at least one vital signs measurement meeting the criteria defined in SAP [Section 2.8.3.2](#).

## 5 Appendix

### 5.1 Imputation rules

#### 5.1.1 AE date imputation

##### 5.1.1.1 AE end date imputation

1. If the AE end date month is missing, the imputed end date should be set to the earliest of the (31DECYYYY, date of death).
2. If the AE end date day is missing, the imputed end date should be set to the earliest of the (last day of the month, date of death).
3. If AE year is missing or AE is ongoing, the end date will not be imputed.

If the imputed AE end date is less than the existing AE start date then use AE start date as AE end date.

##### 5.1.1.2 AE start date imputation

The following table explains the notation used in the logic matrix. Please note that completely missing start dates will not be imputed.

	Day	Month	Year
Partial Adverse Event Start Date	Not used	MON	YYYY
Treatment Start Date	Not used	TRTM	TRTY

The following matrix explains the logic behind the imputation.

	MON MISSING	MON < TRTM	MON = TRTM	MON > TRTM
YYYY MISSING	(1) No convention	(1) No convention	(1) No convention	(1) No convention
YYYY < TRTY	(2.a) Before Treatment Start	(2.b) Before Treatment Start	(2.b) Before Treatment Start	(2.b) Before Treatment Start
YYYY = TRTY	(4.a) Uncertain	(4.b) Before Treatment Start	(4.c) Uncertain	(4.c) After Treatment Start
YYYY > TRTY	(3.a) After Treatment Start	(3.b) After Treatment Start	(3.b) After Treatment Start	(3.b) After Treatment Start

Before imputing AE start date, find the AE start reference date.

1. If the (imputed) AE end date is complete and the (imputed) AE end date < treatment start date then AE start reference date = min (informed consent date, earliest visit date).
2. Else AE start reference date = treatment start date

Impute AE start date -

1. If the AE start date year value is missing, the date uncertainty is too high to impute a rational date. Therefore, if the AE year value is missing, the imputed AE start date is set to NULL.

2. If the AE start date year value is less than the treatment start date year value, the AE started before treatment. Therefore:
  - a. If AE month is missing, the imputed AE start date is set to the mid-year point (01JulYYYY).
  - b. Else if AE month is not missing, the imputed AE start date is set to the mid-month point (15MONYYYY).
3. If the AE start date year value is greater than the treatment start date year value, the AE started after treatment. Therefore:
  - a. If the AE month is missing, the imputed AE start date is set to the year start point (01JanYYYY).
  - b. Else if the AE month is not missing, the imputed AE start date is set to the later of (month start point (01MONYYYY), AE start reference date + 1 day).
4. If the AE start date year value is equal to the treatment start date year value:
  - a. And the AE month is missing the imputed AE start date is set to the AE reference start date + 1 day.
  - b. Else if the AE month is less than the treatment start month, the imputed AE start date is set to the mid-month point (15MONYYYY).
  - c. Else if the AE month is equal to the treatment start date month or greater than the treatment start date month, the imputed AE start date is set to the later of (month start point (01MONYYYY), AE start reference date + 1 day).

If complete (imputed) AE end date is available and the imputed AE start date is greater than the (imputed) AE end date, then imputed AE start date should be set to the (imputed) AE end date.

## **5.2 Statistical models**

No hypothesis testing will be performed for this study.

## **5.3 Rule of exclusion criteria of analysis sets**

Only one analysis set is defined, the FAS. No protocol deviations are defined which lead to exclusion from the FAS.

## **6 Reference**

Not applicable.
